**FOR CD19+, IGA, IGM AND IGG ANALYSIS:**

Study Analysis	Target Day	Study Day	Interval (days)
Visita			
Baseline b	1	≤1	NA
Day 2	2	2	1
Day 3	3	3	1
Week 4	29	15 – 42	28
Week 24	169	106 – 210	98
Week 48	337	≥309	NA

a IgG and IgA will not be collected at Day 2 and Day 3

b If a subject has measurements on the same day as the first infusion date of first dose but at a time after the first infusion of first dose is administered, the measurements will not be defined as baseline, but as Day 2 measurement.

**FOR VITAL SIGNS ANALYSES:**

Study Analysis	Target	Study Dayb	Interval
Visita	Day		(days)
Baseline	NA	Day 1 prior to infusion	NA
Day 1 end of infusion (EOI)	NA	Day 1 after infusion	NA
Day 1 3 hours	NA	Day 1 3 hours after EOI	NA
Day 1 6 hours	NA	Day 1 6 hours after EOI	NA
Week 2	NA	Day 15 prior to infusion	14

Sponsor: Amgen Inc.

Statistical Analysis Plan

Protocol No: 20130108

10-December-2018/ Version 2.0

Day 15 EOI	NA	Day 15 after infusion	NA
Day 15 3 hours	NA	Day 15 3 hours after EOI	NA
Day 15 6 hours	NA	Day 15 6 hours after EOI	NA
Week 24	169	106 – 175	63
Week 26	183	176 – 196	21
Week 30	211	197 – 245	49
Week 48	337	≥309	NA

aIf a visit date with multiple records, the highest value per parameter will be selected for analysis.bDay 1 and Day 15 visit/timepoint are directly associated with infusion date/time.**FOR ADA ANALYSES:**

Study Analysis Visit	Target Day	Study Day	Interval (days)
Baseline a	1	≤1	NA
Week 2	15	2 – 16	15
Week 24	169	106 – 175	63
Week 30	211	197 – 245	49
Week 48	337	≥309	NA

aIf a subject has ADA assessments on the same day as the first infusion date of first dose but at a time after the first infusion of first dose is administered, the ADA assessments will not be defined as baseline, but as Week 2 assessments.

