10.4 Vital Signs

Systolic blood pressure and diastolic blood pressure will be measured on the same arm (preferentially on the left arm) after the subject has been in a supine/sitting position for 5 minutes. Pulse will be recorded simultaneously with blood pressure measurements. Respiration rate and temperature will also be recorded.

During the study, measurement of vital signs may be repeated at the discretion of the Investigator for safety reasons. Clinically relevant abnormal findings will be reported as AEs.

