### **Study Visit**

Since the actual visit for a subject may not exactly coincide with their scheduled visit date, the actual visit date is mapped to the study analysis visit as follows. Note that the following analytical visit windows for statistical analysis are different from the ones defined in Section 18.0 of the IXRS Business Requirement. The actual visit date is allowed to fall within specified interval of the target day.

In general, if more than one actual visit (including the unscheduled visits) falls within the same defined window, the visit closest to the target day with non-missing data will be considered for analysis. If two actual visit dates are at the same distance from the target day, the latest visit with non-missing data will be considered for analysis. For Week 24, only actual visits that occur before or on same date as first infusion of second dose should be considered.

The rules above for selecting a visit from multiple ones within the same visit window are not applicable to retest values of lab data. If the lab measurement is a retest, the retest value will be chosen.

PK concentration will be summarized by the scheduled sample visit in the protocol. For PK concentration collected in the unscheduled visits or in the early discontinuation study visit, the associated scheduled sample visit is defined as below. If multiple records are assigned to the same visit, the one closest to the reference date/time will be selected into the summary.

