### 9.8.3 Laboratory Data

Laboratory test results are reported in International System of Units (SI) units.

Laboratory values and change from baseline will be summarized using descriptive statistics at each analysis visit by treatment. Shift tables of the worst on-study laboratory toxicity based on CTCAE v4.03 grading relative to baseline will be presented by treatment group. The shift tables will take into account all post-baseline (scheduled and unscheduled) laboratory results for determination of worst on-study laboratory toxicity within the two summary timeframes listed previously. For labs with toxicity grading in two directions, for toxicity due to decreased value, the maximum grade is corresponding to the minimum post-baseline value. For toxicity due to increase value, the maximum grade is corresponding to the maximum post-baseline value. In addition, subject incidence tables and listings of grade  $\geq 3$  laboratory toxicities will be provided based on all post-baseline (scheduled and unscheduled) laboratory results for each of the two reporting periods. Standard ranges will be used for the laboratory analysis.

Lab assessments will be grouped for summary as follows:

- Hematology – white blood cell parameters: white blood cell count and differential
- Hematology – red blood cell parameters: hemoglobin, packed cell volume or hematocrit, red blood cell count, mean corpuscular hemoglobin, mean corpuscular hemoglobin concentration
- Hematology – other parameters: platelets
- Serum chemistry – hepatobiliary parameters: alanine aminotransferase (ALT), aspartate aminotransferase (AST), total bilirubin, alkaline phosphatase, gamma glutamyl transferase
- Serum chemistry – general chemistry: sodium, potassium, albumin, total protein, non-fasting glucose
- Serum chemistry – renal function tests: urea, creatinine

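### When a visit date has several vital-sign records, the SAP keeps only the highest value of each parameter, so the lower blood-pressure reading drops out of the vital-sign table

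*SAP*

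**What the plan says.** Footnote a to the vital-sign table in SAP 5.1 (Study Visit) says that, for a visit date with more than one record, "the highest value per parameter will be selected for analysis". It hangs on the visit column as a whole. That column includes the Baseline row and the separate rows for pre-infusion, end of infusion, 3 hours and 6 hours on Days 1 and 15.

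Protocol 10.4 explains why there may be several records: "measurement of vital signs may be repeated at the discretion of the Investigator for safety reasons". It gives no direction, high or low. It then adds: "Clinically relevant abnormal findings will be reported as AEs".

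The selected values feed SAP 9.8.4, which plans descriptive statistics for observed values and change from baseline. Appendix 6 lists one vital-sign output, Table 14-8.1, and no vital-sign listing.

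Laboratory data are treated differently. On retests, SAP 5.1 says: "If the lab measurement is a retest, the retest value will be chosen". On worst on-study grades, SAP 9.8.3 says: "for toxicity due to decreased value, the maximum grade is corresponding to the minimum post-baseline value".

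**The concern.** Vital-sign changes are a stated safety endpoint (Protocol 8.6.1.3, SAP 4.2.4). During the first dose they are taken before each infusion, at its end, and 3 and 6 hours later. In that setting a fall in blood pressure is as much of interest as a rise. Repeats made for safety reasons will tend to cluster where a reading caused concern. A rule that always keeps the highest value treats the two directions unequally: a high reading can never be displaced by its repeat, whereas a low one can. The SAP gives no reason for this, and it does provide for the low direction in laboratory data.

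**Working it through.** The plan states no figure to reproduce. The check is mainly one of logic, followed by an illustration on assumed values.

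**1. Direction of the rule.** With a first reading x1 and a repeat x2, the retained value is max(x1, x2).
- If x2 > x1, the repeat is kept and x1 is dropped.
- If x2 < x1, x1 is kept and the repeat is dropped.
- Either way the lower value goes. With a single record nothing is lost. If both are low, the retained value is still low.

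**2. Whether another vital-sign output recovers it.** SAP 9 includes a minimum among the statistics for continuous variables. Under footnote a, that minimum is the lowest of the retained highest values, not the lowest reading taken. Appendix 6 has listings for grade 3 or higher hematology and chemistry results but none for vital signs.

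**3. Baseline row.** SAP 5.1 (Baseline) takes the latest available value before the first infusion. Suppose there are two pre-infusion readings on Day 1, a and then b, with a > b. The definition gives b and footnote a gives a. Every change from baseline for that subject then differs by a − b, depending on which rule is programmed.

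**4. Date or timepoint.** Days 1 and 15 each have four scheduled timepoints on one date. Read literally, a rule per visit date would pick one value for the whole day, yet the table has four rows for that day. Selection within each timepoint is the natural reading, but it is not stated.

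**5. Illustration (assumed values, none from the documents).** Take systolic pressure with mean 125 mmHg and between-subject SD 15. Let the within-visit SD be s = 5, 8 or 10, with one repeat only when the first reading is below 100 and no real change between readings. The share of first readings below 100 is Φ((100 − 125)/√(15² + s²)). The other columns come from 2,000,000 simulated visits per setting.

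| s | First reading below 100 | Retained value below 100 | Rise in overall mean (mmHg) | Repeat is the one kept |
|---|---|---|---|---|
| 5 | Φ(−1.58) = 5.7% | 3.7% | 0.26 | 68% |
| 8 | Φ(−1.47) = 7.1% | 3.5% | 0.63 | 75% |
| 10 | Φ(−1.39) = 8.3% | 3.6% | 0.98 | 78% |

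The comparison is with keeping the scheduled first record. In this setup the highest value is below 100 exactly when the repeat is, so a rule that kept the repeat would give the same third column. What is peculiar to the highest-value rule is the asymmetry. At the mirror threshold, 125 + 25 = 150 mmHg, the same 5.7% to 8.3% of first readings are high. If those were repeated, all of them would stay in the table, because the maximum cannot be below the first reading.

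**The case against.** The strongest reply is that very little is lost.

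- **The table still shows falls.** Each infusion timepoint has its own row, so a fall recorded once enters unchanged and a fall confirmed by a low repeat remains low. This stands. A reader might infer that the summaries are blind to falls in blood pressure; they are not.
- **Other safety outputs are untouched.** Clinically relevant findings go to AE reporting under Protocol 10.4. SAP Appendix 5 identifies infusion reactions from treatment-emergent AEs by query and date, not from vital-sign values. This stands.
- **The highest value is sometimes the cautious choice**, as for fever, tachycardia or hypertension. This also stands, and it limits the point to parameters where a low value matters.
- **There is no conflict with the general window rule.** A reader might set footnote a against the instruction that "the visit closest to the target day with non-missing data will be considered for analysis". That instruction chooses between visits by distance from a target day. Records on one date are equally distant, and the Day 1 and Day 15 rows have no target day. The laboratory rules are the fair comparison.
- **Repeats are not what the rule removes.** A reader might infer that repeats prompted by a low reading are systematically lost. With no real change, the illustration keeps the repeat in 68% to 78% of cases and usually drops the low reading that prompted it. If pressure truly falls a further 5 or 10 mmHg (s = 8), the repeat is dropped in 42% or 60%.

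None of this supplies a reason for a one-directional rule on blood pressure, or settles the baseline and timepoint questions.

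**Conclusion.** Wrong as written, minor. For parameters where a low value matters, the lower of several same-date readings is dropped by rule from the only planned vital-sign table. The footnote also leaves the Baseline row and the unit of selection (timepoint or date) unclear. The affected output is descriptive, and neither the PK nor the efficacy conclusions depend on it.

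The size cannot be computed: the documents give no repeat rate and no vital-sign variability. The illustration shows direction only. Two stronger statements are tempting but unsupported:
- That means are biased by 0.56 of the within-visit SD. That is the expected maximum of two independent, unselected readings (1/√π = 0.564). It does not describe repeats triggered by the first value, and it would apply only to visits that have repeats.
- That changes from baseline are biased upward. Retained observed values can only be equal or higher, but if footnote a also raises the baseline, the net direction for change is indeterminate.

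**What to change.** Amend footnote a in SAP 5.1 as follows.

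1. For means and changes, select within each scheduled timepoint by a direction-neutral rule: the scheduled record, or the one closest to nominal time.
2. State that the Baseline row follows the baseline definition in SAP 5.1, not the highest value.
3. Where repeats exist, tabulate both the minimum and the maximum post-baseline value for blood pressure and pulse.

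The cost is SAP wording and slightly more table programming. No new data collection is needed.

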## 5.2 PHARMACOKINETIC

Pharmacokinetic parameters will be calculated from serum concentration-time data using noncompartmental analysis (NCA) methods using Phoenix WinNonLin® Version 6.4 or higher (Pharsight Corp, St. Louis, MO). The following PK parameters will be reported for serum rituximab and ABP 798, using actual elapsed sampling times:

Variable	Definition
$C_{max1}$	Maximum observed serum concentration following Dose 1 Infusion 1
$C_{max2}$	Maximum observed serum concentration following Dose 1 Infusion 2
$t_{max1}$	Time to which the maximum serum concentration was observed following Dose 1 Infusion 1
$t_{max2}$	Time to which the maximum serum concentration was observed following Dose 1 Infusion 2
TLST1	Time of last quantifiable concentration following Dose 1 Infusion 1

Sponsor: Amgen Inc.

Protocol No: 20130108

Statistical Analysis Plan

10-December-2018/ Version 2.0

CLST1	Last quantifiable concentration following Dose 1 Infusion 1 over first 14 days postdose (day 15)
AUC 0-14 day	Area under the serum concentration-time curve from time 0 on day 1 prior to the first infusion of the first dose to last quantifiable concentration associated with Dose 1 Infusion 1 over the first 14 days postdose (day 15)
TLST2	Time of last quantifiable concentration associated with Dose 1 Infusion 2
CLST2	Last quantifiable concentration after Dose 1 Infusion 2
AUC 0-12 wk	Area under the serum concentration-time curve from time 0 on day 1 prior to the first infusion of the first dose to last quantifiable concentration over 12-week profile
AUC inf	Area under the serum concentration-time curve from time 0 on day 1 prior to the first infusion of the first dose extrapolated to infinity; calculated as AUC last + CLST2/λ z , where AUC last is the AUC from time 0 to the last quantifiable concentration up to week 12 (i.e. AUC 0-12 wk )
t 1/2	Terminal elimination half-life determined from time 0 to Week 12 profile; calculated as ln(2)/ λ z
λ z	Terminal elimination rate constant
CL	Clearance
AUMC	Area under the first moment curve
MRT	Mean residence time; calculated as AUMC inf /AUC inf – TI /2, where TI represents infusion duration and AUMC inf is the area under the moment curve from the time of first dosing extrapolated to infinity.
AUC 0-12 wk /AUC inf	calculated as AUC 0-12 wk /AUC inf
AUC% extrap	Percent of AUC extrapolated to infinity in AUC inf

Following administration, Cmax, tmax, CLST and TLST will be obtained directly from the experimental observations. If multiple maxima occur at equal concentrations after an infusion, the first temporal value will be used.

AUC0-14 day, AUC0-12 wk and AUCinf will be estimated using the linear trapezoidal rule.

Values of AUC0-14 day and Cmax associated with Dose 1 Infusion 2 will be listed but excluded from descriptive statistics and statistical analysis if the time of the last concentration following Dose 1 Infusion 1 is outside ± 2 day window around Day 15.

Sponsor: Amgen Inc.

Statistical Analysis Plan

Protocol No: 20130108

10-December-2018/ Version 2.0

Values of  $AUC_{0-12\text{ wk}}$  will be listed but excluded from descriptive statistics and statistical analysis if the time of the last concentration following Dose 1 Infusion 2 is outside  $\pm 2$  week window around Week 12.

The terminal half-life,  $t_{1/2}$ , where determined, will be calculated as  $\ln(2)/\lambda_z$ . The number of data points included in the regression will be determined by visual inspection, but a minimum of three data points in the terminal phase, excluding  $C_{\max}$ , will be required to estimate  $\lambda_z$ .  $\lambda_z$  values (and consequently  $t_{1/2}$  and  $AUC_{\text{inf}}$  values) will be considered unreliable estimates if the time period over which an individual  $\lambda_z$  was required is less than twice the resultant  $t_{1/2}$  or the adjusted coefficient of determination 'Rsq' is less than or equal to 0.8. Additional exclusions of PK parameters, if any, will be described in the CSR.

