8.6.1.1 Pharmacokinetic/Pharmacodynamic Endpoints

The primary PK endpoints will be AUC_{inf} and C_{max} following the second infusion of the first dose. Additional PK endpoints will include AUC from time 0 on day 1 prior to the first infusion of the first dose to 14 days postdose (day 15) ($AUC_{0-14\ day}$), AUC from time 0 on day 1 prior to the first infusion of the first dose to week 12 ($AUC_{0-12\ wk}$), and C_{max} following the first infusion of the first dose.

PD endpoints will include the percent of subjects with complete depletion in CD19+ cell count from days 1 to 3.

Table 1. Schedule of Assessments and Procedures

Study Visit/Day/Week D = Day; W = Week	S c n	BL/ D1/ W0	D1 EOI	D1 3 h	D1 6 h	D 2	D 3	D15/ W2	D15 EOI	D15 3 h	D15 6 h	D 16	D 17	W 4	W 8	W 12	W 24 ^a	W 26	W 30	W 40	W48/ EOS ^b			
Visit Window																			± 2 days	± 2 days	± 3 days	± 2 days		
General Assessments																								
Informed consent form	X																							
Medical & medication history	X																							
Physical examination	X	X																	X			X		
Vital signs	X	X	X	X	X					X	X	X	X					X	X	X		X		
ECG	X																							
Chest radiography	X ^c																							
Dosing of ABP 798/ rituximab ^a		X ^d							X ^d										X ^d	X ^d				
Concomitant medication	X	X	X	X	X	X	X	X	X	X	X	X	X	X	X	X	X	X	X	X	X			
AE recording	X	X	X	X	X	X	X	X	X	X	X	X	X	X	X	X	X	X	X	X	X			
Disease Assessments																								
Tender/swollen joint count	X	X																	X	X	X		X	X
Subject and Investigator's global health assessment ^e		X																	X	X	X		X	X
Pain VAS ^e		X																	X	X	X		X	X
HAQ-DI ^e		X																	X	X	X		X	X
Laboratory Assessments																								
Serology (HBsAg, anti-HBc, HCV)	X																							
Serum chemistry	X ^f	X	X						X					X		X		X	X	X		X	X	
Hematology	X	X	X						X					X		X	X		X	X		X	X	

Page 1 of 2

See footnotes on following page.

Table 1. Schedule of Assessments and Procedures

Study Visit/Day/Week D = Day; W = Week	S c n	BL/ D1/ W0	D1 EOI	D1 3 h	D1 6 h	D 2	D 3	D15/ W2	D15 EOI	D15 3 h	D15 6 h	D 16	D 17	W 4	W 8	W 12	W 24 ^a	W 26	W 30	W 40	W48/ EOS ^b	
Visit Window																	± 2 days			± 2 days	± 3 days	± 2 days
Laboratory Assessments (cont'd)																						
CRP	X ^g	X															X	X	X		X	X
ESR	X ^g																					
PK sampling ^h		X	X	X	X	X	X	X	X	X	X	X	X	X	X	X	X	X	X		X	
Antidrug antibodies		X						X									X	X		X		X
CD19+ cell count		X				X	X									X		X				X

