IgA, IgG, and IgM levels		X				X ⁱ	X ⁱ								X		X					X
Urinalysis	X	X						X									X					X
Tuberculosis testing	X																					
Pregnancy ^j	X	X						X								X	X			X	X	
Anti-CCP	X																					
Rheumatoid factor	X																					

Page 2 of 2

AE = adverse event; BL = Baseline; CRP = C-Reactive Protein; EOI = End of Infusion; EOS = End of Study; ESR = Erythrocyte sedimentation rate; h = hour; HAQ-DI = Health Assessment Questionnaire – Disability Index; HBsAg = Hepatitis B surface antigen; Anti-HBc = Hepatitis B core antibody; HCV = Hepatitis C virus antibody; Ig = Immunoglobulin, PK = Pharmacokinetic; Scn = Screening; VAS = Visual analogue scale; Anti-CCP= Anti-cyclic citrullinated peptide antibody

^a The second dose will be administered at week 24 or earlier, ie, anytime from week 16 to week 24, in individual subjects, if necessary in the opinion of the Investigator. For subjects who receive retreatment before week 24, all week 24 and post-week-24 assessments will be moved up to the corresponding time point after treatment (eg, week 26 will be 2 weeks after retreatment, week 30 will be 6 weeks after retreatment, etc.). An infusion may be delayed up to 7 days to allow for recovery from infection.

^b Subjects early terminating study should perform week 48 procedures.

^c Historical radiograph performed within 3 months prior to first dose of IP may be used and does not need to be repeated at screening ([section 10.7](#) for details)

^d ABP 798/rituximab dosing to be administered after all other procedures are completed for each visit.

^e Subjective assessments will be the first procedures performed at the visit.

^f Includes any other lab tests required only for screening. Creatinine clearance calculation will be performed only at screening.

^g Either CRP or ESR is required at screening. CRP will be performed by central lab and results will be blinded to study sites. ESR will be performed by local laboratory.

^h PK sampling: day 1, predose, at EOI, and 3 and 6 hours postdose; day 2 (24 hours postdose); day 3 (48 hours postdose); day 15, predose, at EOI, and 3, 6, and 24 hours postdose (day 16), and 48 hours postdose (day 17). In addition, at week 4 (day 29), week 8 (day 57), week 12 (day 85), and predose week 24, week 26, and week 30, 48/EOS. Blood sampling for PK analysis during each return visit, including the EOS visit, will occur per the scheduled time point with tolerance collection

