### 9.5.2 Pharmacokinetic Parameters

PK parameters for ABP 798 and rituximab will be estimated using noncompartmental analysis methods with Phoenix WinNonlin® Version 6.4 or higher (Pharsight Corp., St. Louis, MO).

In the event that a subject does not receive the full protocol-specified infusion, subsequent PK samples may be considered not evaluable and thus certain PK parameters may not be reportable. In addition, if the full protocol-specified dose was given but there was a long dose interruption or unusually long infusion duration that was deemed to impact PK, the PK profile may be considered not evaluable. The subject exclusion from the PK parameter analysis set will be determined based on a blinded data review prior to unblinding for the final analysis. Any such exclusion will be clearly listed in the CSR along with justification for exclusion.

Pharmacokinetic parameters will be listed by subject and summarized descriptively by treatment for the PK parameter analysis set. The following descriptive statistics will be provided: n, arithmetic mean, SD, Q1, Q3, minimum, median and maximum. Only n, median, Q1, Q3, minimum and maximum will be reported for  $t_{max}$ . In addition, geometric mean, and geometric CV will be calculated for  $AUC_{inf}$ ,  $AUC_{0-14\ day}$ ,  $AUC_{0-12\ wk}$ ,  $C_{max}$ ,  $CLST2$ ,  $t_{1/2}$ ,  $\lambda z$ , CL, MRT,  $AUC\%extrap$  and  $AUC_{last}/AUC_{inf}$ .

The serum PK parameters will be estimated from the individual concentration data for all subjects in the PK parameter analysis set. In estimating the PK parameters, BQL values at

Sponsor: Amgen Inc.

Statistical Analysis Plan

Protocol No: 20130108

10-December-2018/ Version 2.0

the beginning of the profile will be set to zero. BQL values that occur after the first quantifiable point will be considered missing. Actual sampling times will be used in all computations.

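### SAP 5.2 ends AUC0-14day and AUC0-12wk at each subject's last quantifiable sample, so two fixed-interval secondary PK endpoints cover different intervals by subject; the trial-level effect is small

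*SAP*

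**What the plan says.** - **Protocol 8.6.1.1** defines AUC0-14day as "AUC from time 0 on day 1 prior to the first infusion of the first dose to 14 days postdose (day 15" and takes AUC0-12wk from the same origin to week 12. SAP 4.2.1 repeats both as fixed intervals.
- **SAP 5.2** ends AUC0-14day at the last sample, "to last quantifiable concentration associated with Dose 1 Infusion 1 over the first 14 days postdose (day 15", and runs AUC0-12wk "to last quantifiable concentration over 12-week profile". The areas use the linear trapezoidal rule. SAP 9.5.2 adds: "Actual sampling times will be used in all computations".
- **SAP 5.2, acceptance rule.** AUC0-14day is listed but left out of the summaries and the analysis "if the time of the last concentration following Dose 1 Infusion 1 is outside ± 2 day window around Day 15". AUC0-12wk is treated the same way when the "time of the last concentration following Dose 1 Infusion 2 is outside" 2 weeks either side of week 12.
- **Protocol Table 1, footnote a**, attached to the dosing row: "An infusion may be delayed up to 7 days to allow for recovery from infection". The day 15 PK sample is drawn within 1 hour before infusion 2 (Protocol 10.9), so it moves with that infusion.
- **SAP 9.5.2** gives both endpoints a GMR and 90% CI from the model used for the primary parameters.
- **SAP section 10** does not list the changed end point as a departure from the protocol. No visible text interpolates or extrapolates to 14 or 84 days.

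**The concern.** Two subjects with identical exposure can have different values of AUC0-14day only because one had the pre-infusion sample on day 13 and the other on day 17. The label then does not describe the quantity. Variable interval length adds variance that has nothing to do with the product, and if the timing of infusion 2 differed by arm it would add a difference in the GMR unrelated to exposure. A subject whose infusion 2 is 3 to 7 days late, a delay the protocol permits for infection, drops out of the AUC0-14day analysis, although a 14-day area can be approximated from the samples that exist.

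**Working it through.** **Inputs from the documents.** First-interval samples: predose, end of infusion, 3, 6, 24 and 48 hours, then day 15 predose. Day 15 is 14 elapsed days, so ±2 days is 12 to 16 days. Week 12 is 84 elapsed days, so ±2 weeks is 70 to 98 days. Planning CV 40%; 15% dropout, so 85 of 100 per arm.

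**Assumptions.** A 4-hour infusion. Half-life h from 7 to 35 days. The upper end follows from SAP 5.2: the lambda_z period must be at least twice the half-life, and 70 days separate infusion 2 from week 12, so h is at most about 70/2 = 35.

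**1. Reproduce the plan's figure.** The documents state only the primary PK power, above 90%. Log SD = √ln(1 + 0.4²) = 0.385; SE = 0.385 × √(2/85) = 0.0591; ln 1.25/SE − t = 0.2231/0.0591 − 1.654 = 2.12; power ≈ 2Φ(2.12) − 1 = 96.6%. This agrees.

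**2. One subject, AUC0-14day.** With exact mono-exponential integration, the area to T is proportional to 1 − exp(−kT), k = ln 2/h. At h = 18 the values at 12, 14 and 16 days are 0.370, 0.417 and 0.460, which is −11.2% and +10.4% relative to 14 days. With the SAP's linear trapezoid on the protocol's sampling times:

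| Half-life (days) | Ends at 12 d | Ends at 16 d |
|---|---|---|
| 7 | −9.7% | +9.2% |
| 10 | −10.4% | +9.7% |
| 18 | −11.7% | +11.1% |
| 25 | −12.3% | +11.8% |
| 35 | −12.8% | +12.4% |

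A fast distribution phase carrying 30% to 50% of the concentration moves these by less than 1 point. A sample one day off gives about 5% to 6%. The ceiling, for a flat curve, is 2/14 = 14.3%.

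**3. One subject, AUC0-12wk.** Two infusions 14 days apart, exact integration: area proportional to 2 − exp(−kT) − exp(−k(T − 14)). At h = 18 the values at 70, 84 and 98 days are 1.817, 1.893 and 1.938, so −4.0% and +2.4%. At h = 10 the edges are −0.9% and +0.3%; at 25, −6.5% and +4.4%; at 35, −9.0% and +6.8%. Within the protocol's ±2-day week 12 window the error is at most about 1.1%.

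**4. Trial level, balanced timing.** If the end time is uniform over ±2 days with an 11% edge effect, the added SD is 0.11/√3 = 0.064. The total is √(0.385² + 0.064²) = 0.390, and power goes from 96.6% to about 96.1%. This borrows the 40% planning CV for a secondary endpoint.

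**5. Trial level, unbalanced timing.** If 20% of one arm and 10% of another were 2 days late (assumed), with a 10.5% effect each, the GMR shifts by exp((0.20 − 0.10) × ln 1.105) = 1.010.

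**6. Checks on the remedy.**
- SAP 5.2 builds AUCinf as AUClast + CLST2/lambda_z and equates AUClast with AUC0-12wk. If AUC0-12wk were redefined to 84 days and nothing else changed, AUCinf at a 23-day half-life would be misstated by +5.3% (last sample day 70) or −3.5% (day 98).
- Compared with a true day-14 sample, linear interpolation from a day-21 sample overstates AUC0-14day by about 1% to 9% for half-lives of 10 to 23 days. Log interpolation errs by 0% (mono-exponential) to about 3% with a fast phase of up to 40%, and about 4% with one of 50%.

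**The case against.** The strongest objection is that nothing turns on this. The primary endpoints are AUCinf and Cmax after infusion 2, and Protocol 7.2 assesses US/EU similarity on those two. AUC0-14day and AUC0-12wk receive a GMR and CI but no decision. The tolerances are prespecified, excluded values are still listed, and a per-protocol PK sensitivity analysis is planned. Arms are randomised and blinded, and the documents give no reason to expect delays to differ. All of that stands, and it limits the point to a definition that should be tightened.

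The phrase about the first 14 days in SAP 5.2 could also be read as a cap at day 14. That reading fits poorly: under a cap on actual times, the upper half of a ±2-day window would have nothing to accept. The SAP should settle it either way.

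Three stronger inferences are tempting and are not supported:
- **That exposure comparisons are distorted by about 10%.** That is one subject at the window edge; step 5 gives about 1% under an invented imbalance.
- **That the primary analysis is compromised.** AUCinf adds the extrapolated tail after the last sample, so it does not depend on the end time in this way. The same day-15 timing rule also governs exclusion of Cmax after infusion 2, but that value is not an integral, and its exclusion is a separate question.
- **That exclusion follows tolerability.** Footnote a allows the delay for recovery from infection only; it does not mention infusion reactions.

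**Conclusion.** The mismatch is real: the protocol and SAP 4.2.1 fix the intervals, and SAP 5.2 lets them vary by subject. Per subject, AUC0-14day is off by about 9% to 13% at the ±2-day edge. AUC0-12wk at ±2 weeks is off by anything from under 1% at short half-lives to 9% at 35 days. These sizes rest on assumed half-lives of 7 to 35 days, an assumed 4-hour infusion and simple exponential profiles. For the trial the consequence is a little noise, or about 1% in a secondary GMR if delays were unbalanced as assumed. The primary AUCinf and the pooling decision are untouched. The change is a low-priority improvement, worth making because it is cheap.

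**What to change.** In SAP 5.2, before unblinding:

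1. Define AUC0-14day and AUC0-12wk as partial areas to exactly 14.0 and 84.0 days from the start of the first infusion. When a later sample exists (for AUC0-14day, one taken before infusion 2), obtain the end-point concentration by logarithmic interpolation. When the last sample falls short, extrapolate only within the existing tolerance and only if lambda_z is reliable.
2. Keep AUClast, to the actual last quantifiable sample and paired with CLST2, as a separate parameter. Define AUCinf and AUC%extrap from AUClast, so that the primary endpoint does not change.
3. Keep AUC0-14day in the analysis when the pre-infusion-2 sample is late by no more than the 7-day delay the protocol already allows. Flag values more than 2 days late and repeat the analysis without them.

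The cost is SAP wording, a partial-area setting in the PK software, one extra parameter and one repeat analysis. The downside is a few percent of interpolation error in the late subjects, which the repeat analysis covers.
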